#### Analysis Method:

The distribution of MR grade and clinically significant MR at each visit will be summarized using descriptive statistics for categorical variable described in **Section 7.2.** For subjects with paired data, the proportion of subjects in each MR grade change category will be calculated.

- No significant mitral valve (MV) stenosis (measured by echo through 30 days post-procedure)

#### Hypothesis/Decision Criteria:

No specific hypotheses or pass/fail criteria have been set. The analysis will be descriptive and no statistical hypothesis tests are planned.

#### Endpoint Definition/Parameters to Be Estimated:

This endpoint is defined using variables on the core lab echo CRF.

No significant MV stenosis will be assessed by 2 definitions:

- 1) A MV mean gradient  $< 5$  mmHg and effective orifice area (EOA)  $\geq 1.5 \text{ cm}^2$  based on echocardiography core lab data.
- 2) A MV mean gradient  $< 10$  mmHg.

#### Data Collection and Analysis Dataset:

Data will be collected on the core lab echo CRF (either TTE or TTE data, whichever demonstrates a higher MR grade, will be used). Analysis dataset is the Implanted Subjects analysis set.

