### 4.5 Prior to Discharge

Subjects will be cared for through discharge according to standard procedures for mitral valve replacement surgery. Specific anticoagulation/antiplatelet therapy will be prescribed per physician discretion, but is recommended for at least 3-6 months post-implant, and longer unless there is a clinical indication to cease it.

Prior to discharge, the following standard exams and tests will be performed:

- Physical exam and review of adverse events
- TTE and/or TEE evaluation
- ECG
- Blood tests
  - Chemistry profile including creatinine
  - Complete Blood Count
  - CK, CKMB
  - Coagulation panel

- Urinalysis
- Plasma free hemoglobin
- *Cardiac Computed Tomography (CT) – mandatory at US sites only*

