## Appendix A: Schedule of Visits and Procedures

Test / Evaluation	Baseline	Implant Procedure	Discharge	1, 3, 6M (± 2 wks)	12M (± 30 days)	Every 6M (± 30 days) through 5 yrs
Informed Consent	X					
Medical History	X					
Physical Exam (including NYHA Class)	X		X	X	X	X
6-minute walk test	X			X	X	X
Blood Tests: Chemistries (incl. creatinine), CBC, CK/CK-MB, Coagulation panel, plasma free hemoglobin	X	X	X	X	X	X
Pregnancy Test (blood or urine), if appropriate	X					
ECG (12 lead)	X	X	X	X	X	X
Coronary angiogram	X					
Transthoracic Echocardiography (TTE)	X		X 	X 	X 	X 
Transesophageal Echocardiography (TEE)	X	X	X 	X 	X 	X 
Cardiac Computed Tomography (CT)	X		X		X	
Hemodynamics		X				
Quality of Life (QOL) Survey	X				X	
Adverse Events	X	X	X	X	X	X

 TTE or TEE per physician discretion

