## **Appendix B: Participant Information and Consent Form**

## **Appendix C: Instructions for Use**

## Appendix D: Endpoint Definitions

Analysis of study results will include the following additional MVARC defined exploratory endpoints:

**Technical Success** (measures at exit from catheterization laboratory)

All of the following must be present:

- I. Absence of procedural mortality; and
- II. Successful access, delivery, and retrieval of the device delivery system; and
- III. Successful deployment and correct positioning of the first intended device; and
- IV. Freedom from emergency surgery or reintervention related to the device or access procedure

**Device Success** (measured at 30 days and at all later post-procedural intervals):

All of the following must be present:

- I. Absence of procedural mortality or stroke; and
- II. Proper placement and positioning of the device; and
- III. Freedom from unplanned surgical or interventional procedures related to the device or access procedure; and
- IV. Continued intended safety and performance of the device, including:
  - a. No evidence of structural or functional failure
  - b. No specific device-related technical failure issues and complications
  - c. Reduction of MR to either optimal or acceptable levels without significant mitral stenosis (i.e., post-procedure EROA is 1.5 cm^2 with a transmural gradient <5 mm Hg), and with no greater than mild (1+) paravalvular MR (and without associated hemolysis)

**Procedural Success** (measured at 30 days)

All of the following must be present:

- I. Device success (either optimal or acceptable), and
- II. Absence of major device or procedure related serious adverse event, including:
  - a. Death
  - b. Stroke
  - c. Life-threatening bleeding (MVARC scale)
  - d. Major vascular complications
  - e. Major cardiac structural complications
  - f. Stage 2 or 3 acute kidney injury (includes new dialysis)
  - g. Myocardial infarction or coronary ischemia requiring PCI or CABG
  - h. Severe hypotension, heart failure, or respiratory failure requiring intravenous pressors or invasive or mechanical heart failure treatments such as ultrafiltration or hemodynamic assist devices, including intra-aortic balloon pumps or left ventricular or biventricular assist devices, or prolonged intubation for 48 h
  - i. Any valve-related dysfunction, migration, thrombosis, or other complication requiring surgery or repeat intervention

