## Endpoint Definition/Parameters to Be Estimated:

This endpoint is defined using variables on the core lab echo CRF.

The core lab echo CRF will report 7 grade levels of MR: "None", "Trace", "Mild", "Mild-Moderate", "Moderate", "Moderate-Severe", and "Severe". These will be recategorized to the following 5 grade levels of MR: "None/Trace", "Mild" (Mild + Mild-Moderate), "Moderate", "Moderate Severe", and "Severe", with corresponding numerical values of 0, 1, 2, 3, and 4 respectively. For the post-procedure echo, MR grade is defined as the

highest reported severity level of transvalvular leak and paravalvular leak. MR  $\geq 2+$  is considered as clinically significant. The number of grade level changes since baseline will be calculated. There are 4 possible grade change categories: improved (by 1, 2, 3, or 4 grades), no change, and worsened (by 1, 2, 3, or 4 grades).

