#### Analysis Method:

Number and percentage of subjects with no significant MV stenosis at each visit will be calculated as appropriate by definition. Statistics summarizing the distributions of the component endpoints (number and percentage of subjects with MV mean gradient  $\leq 5$  mmHg and  $< 10$  mmHg, number and percentage of subjects with EOA  $\geq 1.5$  cm $^2$ ) will also be presented.

- LVOT patency (measured by echo through 30 days post-procedure)

Hypothesis/Decision Criteria:

No specific hypotheses or pass/fail criteria have been set. The analysis will be descriptive and no statistical hypothesis tests are planned.

Endpoint Definition/Parameters to Be Estimated:

This endpoint is defined using variables on the core lab echo CRF.

LVOT patency is defined as not having an LVOT obstruction. LVOT obstruction is defined as having peak LVOT jet velocity  $\geq 2.7$  m/s (peak instantaneous gradient  $\geq 30$  mmHg) measured by CW Doppler under basal (resting) conditions or physiologically provoked (Valsalva maneuver or post premature ventricular contraction) and having an increment in peak LVOT gradient  $\geq 10$  mmHg from baseline.

Data Collection and Analysis Dataset:

Data will be collected on the core lab echo CRF (either TTE or TTE data, whichever demonstrates a higher degree of LVOT obstruction (equivalent to lowest degree of patency), will be used). Analysis dataset is the Implanted Subjects analysis set.

Analysis Method:

Number and percentage of subjects with LVOT patency at each visit will be calculated. Statistics summarizing the distributions of the component endpoints (number and percentage of subjects with peak instantaneous gradient  $\geq 30$  mmHg, and number and percentage of subjects with an increment in peak LVOT gradient  $\geq 10$  mmHg from baseline) will also be presented.

- Improvement of NYHA Class from baseline (through 30 days post-procedure)

Hypothesis/Decision Criteria:

No specific hypotheses or pass/fail criteria have been set. The analysis will be descriptive and no statistical hypothesis tests are planned.

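### The pilot SAP picks the echo for the mitral stenosis endpoint by MR grade, which is in neither stenosis definition, and picks none when the grades tie

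*Combined protocol and SAP*

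**What the plan says.** The rule is in the SAP for the transapical pilot study (CIP-1403). It is not in the transseptal early feasibility plan bound with it.

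- **Endpoint.** SAP 7.9.2: "No significant MV stenosis will be assessed by 2 definitions". Definition 1 is a mean gradient below 5 mmHg with EOA of at least 1.5 cm². Definition 2 is a mean gradient below 10 mmHg.
- **Exam used for stenosis.** "either TTE or TTE data, whichever demonstrates a higher MR grade, will be used". The MR-grade endpoint in the same section has the identical sentence.
- **MR grade.** After the procedure it is the "highest reported severity level of transvalvular leak and paravalvular leak". The core lab reports seven levels, which the SAP collapses to five.
- **Exam used for LVOT patency.** "whichever demonstrates a higher degree of LVOT obstruction (equivalent to lowest degree of patency), will be used".
- **Which exams are done.** Pilot CIP 4.5 (discharge) and 4.6 (follow-up) both call for "TTE and/or TEE evaluation". The footnote in pilot CIP Appendix A reads "TTE or TEE per physician discretion".
- **Component table.** The stenosis analysis method also reports the "number and percentage of subjects with MV mean gradient" at or below 5 mmHg, and below 10 mmHg. Device success in pilot CIP Appendix D requires absence of stenosis "with a transmural gradient <5 mm Hg", and SAP 7.9.3 uses the same strict limit.
- **Later use.** For the echo endpoints through 5 years, SAP 7.9.3 refers back to 7.9.2 for definition and analysis method, but its own data-collection paragraph has no exam rule. The stenosis element of device success has neither a rule nor a cross-reference.

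**The concern.** A rule that chooses between two exams should use the quantity being reported, or at least one fixed in advance. Here the quantities are gradient and orifice area, while the selector is the severity of leak. The identical wording suggests the sentence was carried over from the MR endpoint.

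Two consequences follow at a visit with both exams. Stenosis status can come from either exam, for a reason that neither definition contains. When the MR grades agree, the SAP names no exam, so the analyst has to choose after seeing the data. This is one of five secondary performance endpoints. No hypothesis is tested, so the reported percentages are themselves the result.

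The component table raises a separate question, which does not depend on having two exams: its cutoff is not the cutoff in the definition.

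**Working it through.** The plan gives no figure to reproduce: the sample size is not statistically derived and there is no pass criterion. The check is therefore one of logic, plus one line of arithmetic.

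**1. Selector against definition (SAP 7.9.2).**

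| Endpoint | Judged on | Exam selected by |
|---|---|---|
| MR reduction | MR grade | higher MR grade |
| LVOT patency | LVOT velocity and gradient | greater LVOT obstruction |
| No significant stenosis | mean gradient; EOA in definition 1 | higher MR grade |

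Only the stenosis row is keyed to another endpoint's variable. The SAP version 3.0 history entry says that the greater severity between TTE and TEE is to be reported where applicable. I use it only as evidence of intent. It also supports reading the repeated TTE as TTE or TEE.

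**2. Can the choice matter?** The values below are assumed, to test the rule.

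- Definition 1: exam A has MR 0, 6 mmHg, 1.3 cm²; exam B has MR 1, 4 mmHg, 1.8 cm². The rule picks B, so no stenosis is reported. Exam A has stenosis.
- Definition 2: exam A has MR 0, 11 mmHg; exam B has MR 1, 8 mmHg. The rule picks B, so no stenosis is reported. Exam A has stenosis.
- Swap the MR grades in either example and the rule picks the more stenotic exam.

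**3. Enumeration.** Take MR grades 0–4, gradients 3, 4, 6, 8 and 11 mmHg, and EOA 1.3 and 1.8 cm² (an assumed grid). That gives 5 × 5 × 2 = 50 exam profiles and 50 × 50 = 2,500 ordered pairs.

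- Definition 1 is met by 10 profiles (3 or 4 mmHg with 1.8 cm², at five MR grades). Discordant pairs: 2 × 10 × 40 = 800.
- Definition 2 is met by 40 profiles. Discordant pairs: 2 × 40 × 10 = 800.
- For each definition, of the 800 discordant pairs the rule takes the less stenotic exam in 320, the more stenotic in 320, and neither in 160, where MR grades are equal.

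The symmetry comes from the grid. The counts show that the rule does not order exams by stenosis as the SAP defines it. They do not estimate how often this will happen.

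**4. Ties.** For the MR endpoint a tie is harmless, because both exams give the same grade. For stenosis it leaves status undefined whenever the two exams fall on opposite sides of a cutoff. The SAP does not say whether the seven-level or the five-level scale drives selection. The five-level scale merges None with Trace and Mild with Mild-Moderate, so it ties more often.

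**5. Size per subject.** One subject changes a percentage by 100/n points. At the cap of 95 treated subjects (SAP section 6), 100/95 = 1.05. At the interim looks of 75 and 50 subjects (SAP 7.8), 100/75 = 1.33 and 100/50 = 2.0. Denominators are implanted subjects with data, so 1.05 is a floor. The number of subjects affected cannot be obtained from the documents.

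**6. The 5 mmHg boundary.** A subject with a mean gradient of exactly 5 mmHg counts as meeting the tabulated component (5 or less) and fails definition 1 (below 5). The same sentence tabulates the second cutoff strictly, below 10, in agreement with definition 2.

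**The case against.** The strongest reply concerns the remedy. Taking the higher of two noisy gradients does not bring the result closer to true valve status; it leans towards reporting stenosis. The greater-severity convention is inferred from two other endpoints and a history note limited to applicable cases. Naming one primary modality would also give a defined rule. It stands that the change cannot be defended as more accurate. It does not stand that the choice is mere taste: selecting on the endpoint's own severity is what the SAP does for MR and LVOT.

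Second, device success combines MR level and absence of stenosis in one echo criterion. Selecting by gradient for one and by MR for the other could mix two exams. That is correct and should be settled in the text.

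Third, the footnote in pilot CIP Appendix A suggests that most visits have one exam, and everything is descriptive. This stands and sets the weight of the point.

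Fourth, the component cutoff and the repeated TTE are separate slips that do not strengthen the main point. That also stands; they are listed because they sit in the same paragraphs.

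A reader might also infer that the 5-year stenosis endpoint has no exam rule at all. The back-references in SAP 7.9.3 to both the definition and the methods of 7.9.2 make carry-forward the natural reading. Only device success has no such link.

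**Conclusion.** The point holds and is minor. For the stenosis endpoint the SAP states a selection rule keyed to a variable in neither definition, against its own convention. At visits with both exams the rule can report either the less or the more stenotic one, and at equal MR grades it reports neither. Each reclassified subject moves the percentage by about 1.1 points at 95 subjects. How many would be reclassified is not known and is probably few. Separately, the component table contradicts definition 1 at exactly 5 mmHg.

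The point rests on reading the repeated TTE as TTE or TEE, and on some visits having both exams, which the pilot CIP permits.

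A reader might infer that the rule inflates the no-stenosis rate. The documents do not support that: the rule can err either way, and they give no data on how MR grade and gradient differ between paired exams. Nor do they establish that MR grade carries no information on gradient; they show only that it is in neither definition. With no test and no pass criterion, no trial conclusion is overturned.

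**What to change.** In the stenosis data-collection paragraph of SAP 7.9.2, replace the selection phrase with: TTE or TEE data, whichever shows the higher core-lab mean gradient, with EOA taken from that same exam; if the gradients are equal, the exam with the smaller EOA.

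Then:

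- State that this rule also governs the stenosis endpoint through 5 years and the stenosis element of device success (SAP 7.9.3).
- State that within device success the MR and stenosis elements are each judged on the exam showing greater severity for that element.
- Tabulate the gradient component at below 5 mmHg.
- Correct the repeated TTE to TTE or TEE in the MR, stenosis and LVOT paragraphs.

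The cost is SAP wording and light reprogramming on existing core-lab data. The reported no-stenosis rate may be slightly less favourable. If the selected exam has no EOA and a gradient below 5 mmHg, definition 1 is missing at that visit under SAP 7.4; the current rule has the same limitation. Ranking by gradient first can pass over a smaller EOA on the other exam, which is the price of one rule for both definitions with both measurements from one exam. The gain is a defined rule that matches the SAP's convention.

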#### Analysis Method:

Number and percentage of subjects with no significant MV stenosis at each visit will be calculated as appropriate by definition. Statistics summarizing the distributions of the component endpoints (number and percentage of subjects with MV mean gradient  $\leq 5$  mmHg and  $< 10$  mmHg, number and percentage of subjects with EOA  $\geq 1.5$  cm $^2$ ) will also be presented.

- LVOT patency (measured by echo through 30 days post-procedure)

Hypothesis/Decision Criteria:

No specific hypotheses or pass/fail criteria have been set. The analysis will be descriptive and no statistical hypothesis tests are planned.

Endpoint Definition/Parameters to Be Estimated:

This endpoint is defined using variables on the core lab echo CRF.

LVOT patency is defined as not having an LVOT obstruction. LVOT obstruction is defined as having peak LVOT jet velocity  $\geq 2.7$  m/s (peak instantaneous gradient  $\geq 30$  mmHg) measured by CW Doppler under basal (resting) conditions or physiologically provoked (Valsalva maneuver or post premature ventricular contraction) and having an increment in peak LVOT gradient  $\geq 10$  mmHg from baseline.

Data Collection and Analysis Dataset:

Data will be collected on the core lab echo CRF (either TTE or TTE data, whichever demonstrates a higher degree of LVOT obstruction (equivalent to lowest degree of patency), will be used). Analysis dataset is the Implanted Subjects analysis set.

Analysis Method:

Number and percentage of subjects with LVOT patency at each visit will be calculated. Statistics summarizing the distributions of the component endpoints (number and percentage of subjects with peak instantaneous gradient  $\geq 30$  mmHg, and number and percentage of subjects with an increment in peak LVOT gradient  $\geq 10$  mmHg from baseline) will also be presented.

- Improvement of NYHA Class from baseline (through 30 days post-procedure)

Hypothesis/Decision Criteria:

No specific hypotheses or pass/fail criteria have been set. The analysis will be descriptive and no statistical hypothesis tests are planned.

## Endpoint Definition/Parameters to Be Estimated:

This endpoint is defined using variables on the baseline and follow-up CRFs.

NYHA class ranges from Class I to IV. The classes describe increasingly limited physical activity. The number and percentages of subjects who died prior to visit, as well as the number of classes changed from baseline through 30 days post-procedure for subjects with paired data, will be calculated.

## Data Collection and Analysis Dataset:

Data will be collected on the screening and follow-up CRFs. Data will be summarized on the Attempted Subjects analysis set.

## Analysis Method:

The NYHA class will be summarized as a categorical variable at each visit, and for subjects with paired data, change from baseline will be summarized both as a categorical and a continuous variable using appropriate statistics described in **Section 7.2**.

### **7.9.3 Additional Exploratory Endpoints**

Event and endpoint definitions for this study's analysis will be based on those definitions outlined in the MVARC Consensus Document. Each subject's data will be reviewed individually and case summaries for all subjects will be provided. These endpoints are listed only in the CIP for the US and France.

- Measured by echo post-procedure through 5 years:
  - Reduction in MR Grade from baseline
  - No significant MV stenosis
  - LVOT patency
  - Improvement in LVEF
  - Improvement in cardiac output/cardiac index
  - Reduction in LV end-systolic and end-diastolic dimensions

## Hypothesis/Decision Criteria:

No specific hypotheses or pass/fail criteria have been set. The analysis will be descriptive and no statistical hypothesis tests are planned.

## Endpoint Definition/Parameters to Be Estimated:

This endpoint is defined using variables on the core lab echo CRFs.

Reduction in MR grade from baseline, No significant MV stenosis, and LVOT patency have been defined in **Section 7.9.2**. Improvement in LVEF is defined as a higher LVEF (%) compared to a reference value. Improvement in cardiac output/cardiac index is defined as a higher cardiac output/cardiac index compared to a reference value. Reduction in LV end-systolic and reduction in LV end-diastolic dimensions will be calculated separately. The reference values are collected at baseline.

Change from baseline will be calculated using available data on the analysis set at each follow-up visit. Possible changes are “improved”, “no change” and “worsened”.

#### Data Collection and Analysis Dataset:

Data will be collected on the screening and follow-up CRFs. Data will be summarized on the Implanted Subjects analysis set.

#### Analysis Method:

MR grade, presence/absence of significant MV stenosis, LVOT patency and component endpoints will be summarized using analysis methods described in **Section 7.9.2**. LVEF, cardiac output/cardiac index, and LV end-systolic and end-diastolic dimensions will be summarized using descriptive statistics for continuous variables by visit. For subjects with paired data, change from baseline will also be summarized using appropriate statistics described in **Section 7.2** by visit.

- Change in 6MWT from baseline through 5 years

#### Hypothesis/Decision Criteria:

No specific hypotheses or pass/fail criteria have been set. The analysis will be descriptive and no statistical hypothesis tests are planned.

#### Endpoint Definition/Parameters to Be Estimated:

This endpoint is defined using variables on the baseline and follow-up CRFs.

Change in 6MWT from baseline is defined as the difference between the distance (in meters) a subject walks in 6 minutes at baseline and a later visit.

#### Data Collection and Analysis Dataset:

Data will be collected on the baseline and follow-up CRFs. Data will be summarized on the Attempted Subjects analysis set.

#### Analysis Method:

6MWT will be summarized using descriptive statistics for continuous variable described in **Section 7.2** by visit. For subjects with paired data, change in 6MWT from baseline will also be summarized using descriptive statistics for continuous variable described in **Section 7.2** by visit.

- Change in quality of life (MLHFQ) from baseline to 12 months

Hypothesis/Decision Criteria:

No specific hypotheses or pass/fail criteria have been set. The analysis will be descriptive and no statistical hypothesis tests are planned.

Endpoint Definition/Parameters to Be Estimated:

This endpoint is defined using variables on the baseline and follow-up CRFs.

The MLHFQ has a total score that can range from 0 to 105. A lower score indicates a higher quality of life. A negative change during follow-up compared to baseline represents an improvement in quality of life.

Change in MLHFQ from baseline is defined as the difference between a subject's score at baseline and a later visit.

Data Collection and Analysis Dataset:

Data will be collected on the baseline and 12-month follow-up CRFs. Data will be summarized on the Approved Subjects analysis set.

Analysis Method:

MLHFQ score will be summarized using descriptive statistics for continuous variable described in **Section 7.2** by visit. For subjects with paired data, change in MLHFQ score from baseline will also be summarized using descriptive statistics for continuous variable described in **Section 7.2** by visit.

- Change in NYHA from baseline through 5 years

Hypothesis/Decision Criteria:

No specific hypotheses or pass/fail criteria have been set. The analysis will be descriptive and no statistical hypothesis tests are planned.

Endpoint Definition/Parameters to Be Estimated:

This endpoint is defined using variables on the baseline and follow-up CRFs.

Change in NYHA class from baseline is defined as the difference between a subject's NYHA class at baseline and a later visit. The number and percentages of subjects who died prior to visit, as well as the number of classes changed from baseline at each follow-up visit will be calculated for subjects with paired data.

